## 1. SYNOPSIS

|  |  |   |
|--|--|---|
| Study Title                     | SCar location and Acute haemodynamic Response to MultiPoint Pacing in patients with cardiomyopathy   |   |
| Internal ref. no. / short title | Scar MPP study  |   |
| Study Design                    | Pilot study  |   |
| Study Participants              | Patients with left ventricular myocardial scar and clinical indication to implant of a Cardiac Resynchronization Therapy- Defibrillator (CRT-D) device                         |   |
| Planned Sample Size             | 15 patients  |   |
| Planned Follow-up duration      | 1 day  |   |
| Recruitment end date            | 31 st June 2020   |   |
|  | Objectives  | Outcome Measures   |
| Primary                         | To assess whether the added benefit of multipoint pacing (MPP) over conventional single-site LV pacing is consistent in the peri-scar region compared to the remote myocardium | 
 
- Acute haemodynamic response to MPP (percentage increase of LV-dP/dTmax produced by MPP over spontaneous ventricular activation) in the peri-scar region and in the remote myocardium
 
- Percentage increase of LV dP/dTmax produced by MPP over conventional single-site LV pacing in the peri-scar region and in the remote myocardium
 
 |

|  |                                    |                                      |
|--|------------------------------------|--------------------------------------|
| Subject: Research protocol                    | Short Title: SCAR MPP study | Chief Investigator: [name] |
| Version/Date: 1.1 /6 th April 2019 | IRAS Ref: 211326            | Ethics Ref: 16/SC/0662        |
| Page 4 of 27                                  |                                    |                                      |

## 2. ABBREVIATIONS

|              |  |
|--------------|--|
| AHR          | Acute Haemodynamic Response  |
| BiV          | Biventricular  |
| CRM          | Cardiac Rhythm Management  |
| CRT          | Cardiac Resynchronization Therapy  |
| CS           | Coronary sinus   |
| GP           | General practitioner   |
| LV           | Left ventricle/ ventricular  |
| MPP          | MultiPoint Pacing  |
| LV-dP/dT max | Maximal (max) rate of rise of left ventricular pressure (LV-dP) over time (dT) |
| MRI          | Magnetic Resonance Imaging   |
| NHS          | National Health System   |
| OUH          | Oxford University Hospitals  |
| QoL          | Quality of Life  |
| RV           | Right ventricle/ventricular  |
| SOP          | Standard Operating Procedure   |

|  |                                    |                                      |
|--|------------------------------------|--------------------------------------|
| Subject: Research protocol                    | Short Title: SCAR MPP study | Chief Investigator: [name] |
| Version/Date: 1.1 /6 th April 2019 | IRAS Ref: 211326            | Ethics Ref: 16/SC/0662        |
| Page 5 of 27                                  |                                    |                                      |

#### 4. BACKGROUND AND RATIONALE

Many patients with cardiomyopathy and heart failure have an abnormality of the heart's electrical system resulting in an uncoordinated (asynchronous) contraction pattern of the bottom chambers of the heart (electrical dissynchrony). This further reduces the pumping ability of a weakened heart muscle.

Cardiac resynchronization therapy (CRT) is a widely accepted treatment option in these patients. It works by sending tiny electrical impulses to the bottom chambers (ventricles) of the heart to make them beat together again in a more synchronised pattern. The heart's ability to pump blood and oxygen to the body is so improved.

A CRT device consists of a unique type of cardiac pacemaker which has two or three electrodes (or leads), one in the right ventricle, one in one of the branches of a vein on the outer surface of the left ventricle (called coronary sinus or CS), and often one in the right atrium (right top chamber, in order to ensure also synchronism between top and bottom chambers) (fig 1).

[figure not shown]

Fig 1. CRT device components.

The simultaneous activation of the left and right ventricle can restore a coordinated, or synchronous, pumping action (1). In most patients CRT improves symptoms of heart failure and quality of life, reduces the chance of being admitted to hospital with worsening heart failure, it makes people live longer (2,3).

The implant procedure usually takes a few hours and it is performed under X-ray guidance. Local anaesthetic is injected into the upper chest wall, most commonly on the left side. An incision is made and a pocket is created under the skin. A venous blood vessel is punctured under the clavicle and pacing leads are guided through it into the heart chambers. A contrast injection (venogram) is usually performed in the coronary sinus in order to identify its branches and guide the placement of the LV lead. The leads are attached to the generator box, or battery, and all device components are placed into the pocket. The site is then sutured either with dissolvable or not dissolvable sutures which if the later, need to be removed 7-10 days post procedure. A chest x-ray and a pacing check are carried out post procedure to ensure that the pacing leads are in the correct position, and that the pacemaker is functioning correctly.

Once implanted, the device needs to be worn permanently and stimulate the heart continuously in order to keep its positive effects on heart function. The battery needs to be replaced every few years (depending on

|  |                                    |                                      |
|--|------------------------------------|--------------------------------------|
| Subject: Research protocol                    | Short Title: SCAR MPP study | Chief Investigator: [name] |
| Version/Date: 1.1 /6 th April 2019 | IRAS Ref: 211326            | Ethics Ref: 16/SC/0662        |

amount of pacing and battery characteristics); the leads do not need replacement unless in case of malfunction.

Although most patients have a significant improvement from CRT therapy, up to one third of patients do not benefit from it and to date there are no useful criteria to predict the response to CRT (4).

In an effort to improve CRT response, alternative methods of CRT delivery have been developed. One potential strategy to improve response is multisite left ventricular (LV) stimulation, i.e. simultaneous stimulation of more than one area of the left ventricle in addition to right ventricular (RV) pacing.

In this scenario, a new pacing feature has been recently become available that allows simultaneous LV stimulation from two different sites by means of a single lead with four electrodes (quadripolar lead). It is called MultiPoint Pacing (MPP; St. Jude Medical, Sylmar, CA) and it is available for some CRT devices in combination with a quadripolar LV lead. Both the devices with MPP and the quadripolar leads are already widely used as part of standard care and they are CE-marked. Of note, they are already used as standard care at Oxford University Hospitals (OUH) NHS Foundation Trust.

Simultaneous excitation of a larger mass or volume of cardiac tissue through MPP should theoretically result in faster depolarization velocity and early depolarization of sites of late intrinsic activation, with shorter LV trans-ventricular conduction times, better synchronization and increased cardiac output (5-7).

Although the MPP technology has a proven safety and efficacy profile comparable to the other CRT technology, evidence regarding the long term additional benefits of this pacing modality over conventional single site LV pacing is lacking. To this aim, a randomized multicentre study (MORE CRT MPP study) is currently underway to show the superiority of MPP over conventional single site LV pacing.

Some data are available about acute effects of MPP, i.e. the acute change in cardiac haemodynamics as MPP is activated.  $LV-dP/dT_{max}$ , consisting in the maximal rate of rise of LV pressure during cardiac contraction, is often measured to this aim. Basically a pressure manometer wire is temporarily placed into the LV during the CRT procedure and it continuously measures the left ventricular pressure. Studies investigating the Acute Haemodynamic Response (AHR) of MPP over conventional single site LV pacing with this or other techniques have documented small, variable and often not clinically significant improvements from MPP compared to single site LV pacing.

Study sub-analyses seem to suggest that MPP pacing could be particularly beneficial in specific subgroups of patients (12) and when stimulating particular areas of the LV, with up to 35-40% improvement in  $LV-dP/dt_{max}$  if compared to conventional single-site LV pacing in the same site (13). Studies using biophysical modelling suggest that MPP from a quadripolar lead may exert its benefit mainly in patients with ischaemic heart disease resulting in LV scar (14).

In order to optimize the response rate to CRT, it is extremely important to understand how MPP works, which subgroup of patients may benefit more from it and if a specific LV location should be chosen in order to have an added benefit from it. Of note, this pacing feature requires specific devices and higher energy, with increased battery drainage leading to more frequent battery changes and increased risk of infections so it is really important to understand when it is worth using it.

|  |                                    |                                      |
|--|------------------------------------|--------------------------------------|
| Subject: Research protocol                    | Short Title: SCAR MPP study | Chief Investigator: [name] |
| Version/Date: 1.1 /6 th April 2019 | IRAS Ref: 211326            | Ethics Ref: 16/SC/0662        |
| Page 8 of 27                                  |                                    |                                      |

### 3.1 Research question and hypothesis

We plan to investigate if the added benefit of MultiPoint Pacing over conventional single-site LV pacing is related to the presence of scar in the left ventricle and the position of the pacing lead relative to it.

Our hypothesis is that MMP produces a better AHR compared to conventional single site LV pacing if there is scar in the left ventricle and when the lead is placed closed to the scar because this allows the recruitment of large areas of peri-scar viable tissue, characterized by slow conduction, with quicker electrical activation and more vigorous contraction (fig.2).

[figure not shown]

Fig.2. When positioned at sites of healthy myocardium, MPP gives no incremental benefit over conventional single site LV pacing because there are no areas of slow conduction and block (left panel). On the other hand, when the LV lead is positioned next to myocardial scar, where there are areas of slow ventricular conduction and block, MPP can improve the electrical activation by recruiting more tissue at the same time (right panel).

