## 5. STUDY DESIGN

A prospective single-centre pilot study will be conducted to investigate this topic. Fifteen patients with both ischemic and non-ischemic cardiomyopathy resulting in left ventricular myocardial scar and elected to CRT implant at the OUH, will be enrolled in this study.

Compared to standard practice, additional research investigations will be a baseline visit for eligibility assessment, informed consent and pre-CRT implant cardiac MRI, a three-dimensional electroanatomical map reconstruction of the CS venous system during the standard CRT implant and the evaluation of the acute haemodynamic response (AHR, percentage increase of LV-dP/dT max) of MPP over conventional single-site LV pacing during the CRT implant.

1. The cardiac Magnetic Resonance Imaging (MRI) will be performed in each patient 1-2 weeks before the CRT implant during the baseline visit. It will provide information regarding left ventricular (LV) function and volumes, characterization of LV tissue, presence and location of myocardial scar, anatomy of the CS venous system. Moreover, the peri-scar region (viable tissue immediately close to the scar) and the remote

|  |                                    |                                      |
|--|------------------------------------|--------------------------------------|
| Subject: Research protocol                    | Short Title: SCAR MPP study | Chief Investigator: [name] |
| Version/Date: 1.1 /6 th April 2019 | IRAS Ref: 211326            | Ethics Ref: 16/SC/0662        |

myocardium (viable tissue farther from it) will be identified according to a 17-segments LV segmentation model (see intervention section for more details).

2. A de-novo CRT implant will be performed under fluoroscopic guidance as per standard care. All subjects will be implanted with a regulatory approved St. Jude Medical CRT device compatible with MPP feature (models n° CD3271-40(Q), CD3371-40(Q), CD3371-40C(QC) or newer) and St. Jude Medical quadripolar left ventricular lead (Quartet 1458Q or newer). The choice of the right ventricular and right atrial leads will be left to the operator. After implant of the right ventricular and right atrial leads, a CS venogram will be then performed as per standard practice (see intervention section for more details).

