## 6. OBJECTIVES AND OUTCOME MEASURES

| Objectives   | Outcome Measures  | Timepoint(s) of evaluation of outcome measure |
|--|---|---|
| Primary

To assess whether the added benefit of multipoint pacing (MPP) over conventional single-site LV pacing is consistent in the peri-scar region compared to the remote myocardium | - Acute haemodynamic response to MPP (percentage increase of LV- dP/dTmax produced by MPP over spontaneous ventricular activation) in the peri-scar region and in the remote myocardium

- Percentage increase of LV dP/dT max produced by MPP over conventional single-site LV pacing in the peri-scar region and in the remote myocardium | CRT-D implant procedure                       |

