### 8.2. Inclusion Criteria

- Age of 18 years or over
- Left ventricular myocardial scar;
- Standard indication to CRT-D (NYHA functional class III-IV despite optimal medical therapy, LV ejection fraction (LVEF) ≤35 %, QRS duration ≥120 msec, LBBB);
- Will and ability to give informed consent for participation in the study.

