### **12.3. Analysis of Outcome Measures**

The following measurements will be collected and analysed:

- LV-dP/dTmax during spontaneous ventricular rhythm;
- LV-dP/dTmax during single site LV pacing in 4 different pacing configurations (4 different poles used in turn), with the LV lead either in the peri-scar CS branch or in the remote myocardium CS branch. The pacing configuration producing the biggest LV-dP/dTmax over spontaneous ventricular rhythm will be considered the best pacing configuration in each CS branch and used for further comparisons and analyses;
- LV-dP/dTmax during single MPP LV pacing in 3 different configurations, with the LV lead either in the peri-scar CS branch or in the remote myocardium CS branch. The pacing configuration producing the biggest LV-dP/dTmax will be considered the best pacing configuration in each CS branch and used for further comparisons and analyses.

|  |                                    |                                      |
|--|------------------------------------|--------------------------------------|
| Subject: Research protocol                    | Short Title: SCAR MPP study | Chief Investigator: [name] |
| Version/Date: 1.1 /6 th April 2019 | IRAS Ref: 211326            | Ethics Ref: 16/SC/0662        |

The percentage change in LV-dP/dTmax produced by the best single site LV pacing configuration over spontaneous ventricular rhythm will represent the best Acute Haemodynamic Response (AHR) of single site LV pacing in each CS branch. The percentage change in LV-dP/dTmax produced by the best MPP LV pacing configuration over spontaneous ventricular rhythm will represent the best Acute Haemodynamic Response (AHR) of MPP LV pacing in each CS branch.

The following comparisons will be made as outcome measures:

- AHR produced by the best MPP configuration in the peri-scar region versus AHR produced by best MPP configuration in the remote myocardium;
- percentage increase of LV-dp/dTmax produced by the best MPP configuration over single site LV pacing in the peri-scar region versus percentage increase of LV-dp/dTmax produced by the best MPP configuration over the best conventional single-site LV pacing in the remote myocardium.

Our hypotheses are that:

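### Every patient has scar and only peri-scar versus remote comparisons are planned, so Section 3.1's scar-presence question cannot be answered and its claim of MPP benefit near scar has no planned test or interval

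*Combined protocol and SAP*

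**What the plan says.** Section 3.1 names two factors. It asks whether the extra benefit of MPP "is related to the presence of scar in the left ventricle and the position of the pacing lead relative to it". The hypothesis that follows is that "MMP produces a better AHR compared to conventional single site LV pacing if there is scar in the left ventricle" and the lead is near that scar. The Fig. 2 legend adds that at healthy sites "MPP gives no incremental benefit over conventional single site LV pacing because there are no areas of slow conduction and block".

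Section 5 enrols "Fifteen patients with both ischemic and non-ischemic cardiomyopathy resulting in left ventricular myocardial scar", and Section 8.2 lists "Left ventricular myocardial scar" as an inclusion criterion.

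The primary objective in Section 6 is whether the added benefit "is consistent in the peri-scar region compared to the remote myocardium". Its second outcome is the percentage increase "produced by MPP over conventional single-site LV pacing in the peri-scar region and in the remote myocardium", so the gain of MPP over single-site pacing is recorded separately in each zone.

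Section 12.3 lists two comparisons. The first is "AHR produced by the best MPP configuration in the peri-scar region versus AHR produced by best MPP configuration in the remote myocardium". The second sets the MPP-over-single-site gain near scar against the same gain in remote myocardium. The hypotheses closing Section 12.3 have the same form, peri-scar higher than remote. Section 12.2 describes the test only as a comparison of the two pacing sites.

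**The concern.** The question and hypothesis in Section 3.1 go further than the design and analysis in two places.

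First, an effect of having scar needs ventricles with and without it, and this study has only the former. Remote myocardium, defined in Section 9.2.3 as viable tissue two or more segments from scar, lies in the same scarred ventricle. It is a comparator for lead position, not for the absence of scar.

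Second, that MPP beats single-site pacing near scar is a statement about one zone: the mean gain there exceeds zero. The planned comparisons ask whether one zone exceeds the other, and neither answer implies the other.

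Section 12.1 says the pilot is meant to confirm the validity of its hypothesis for a larger study. Section 4 says MPP drains the battery faster and that it matters to know when it is worth using. That depends on the size of the gain near scar, not only on its difference from the gain elsewhere.

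**Working it through.** **Which part of Section 3.1 each planned analysis reaches**

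| Part of Section 3.1 | Contrast needed | Planned? |
|---|---|---|
| Presence of scar | Patients with v without scar | No; 0 of 15 scar-free, not estimable |
| Lead position relative to scar | Gain near scar minus gain in remote tissue | Yes, second comparison in 12.3 |
| MPP better than single-site near scar | Gain near scar v 0 | Measured (Section 6), but no test or interval |

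The first comparison in Section 12.3 uses no single-site data. It could favour the peri-scar branch because that branch responds better to pacing of either kind.

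**The plan's own figure.** Section 12.1 says 15 patients could be enough for 80% power at 95% confidence, citing gains from 0% to 40% by site. No SD is given, so this can be neither reproduced nor refuted. Reading it as a 40-point difference, a paired two-sided t-test with n = 15 needs a standardised difference of 0.778 for 80% power. The implied SD of the differences is 40 / 0.778 = 51.4 points. In either case the statement concerns the difference between zones.

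**What the between-zone difference shows.** Let G_p and G_r be the mean gains of MPP over single-site pacing near scar and in remote tissue. The second comparison estimates D = G_p - G_r.

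- G_p = +8, G_r = 0: D = 8, and MPP is better near scar.
- G_p = 0, G_r = -8: D = 8, and MPP adds nothing near scar.
- G_p = +5, G_r = +5: D = 0, and MPP is better near scar.

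**How often this could occur.** Assumptions not in the documents: normal gains, equal SD in each zone, correlation 0.5, n = 15, paired two-sided 5% test. At correlation 0.5 the SD of the difference equals the per-zone SD, since sqrt(2 × SD² × (1 - 0.5)) = SD. The columns give the simulated percentage of trials in which the result is significant in the peri-scar direction.

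| True G_p, G_r | SD per zone | Zone test | Peri-scar gain v 0 | Both |
|---|---|---|---|---|
| 0, -5 | 5 | 95% | 2.5% | 2.5% |
| 0, -5 | 10 | 44% | 2.5% | 2.1% |
| +5, +5 | 5 | 2.4% | 95% | 2.4% |
| +5, +5 | 10 | 2.6% | 44% | 2.2% |
| +8, 0 | 5 | >99% | >99% | >99% |
| +8, 0 | 10 | 82% | 82% | 71% |

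**Precision of the missing interval.** The 95% half-width is t(0.975, 14) × SD / sqrt(15) = 2.145 × SD / 3.873. For SDs of 5, 10, 15 and 20 points it is 2.8, 5.5, 8.3 and 11.1 points. The gain detectable with 80% power is 0.778 × SD: 3.9, 7.8, 11.7 and 15.6 points.

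**Selection bias in the gain.** Sections 9.2.4 and 12.3 take the best of 3 MPP settings and the best of 4 single-site settings. If all settings had the same true response and independent normal errors, the expected maxima are 0.85 and 1.03 error SDs. The gain is then biased by 0.85 - 1.03 = -0.18 error SDs, against MPP. If the error SD is the same in both zones this cancels in D, but it stays in each zone's own gain.

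**The case against.** The fair reply is that Section 3.1 is introductory and the operative plan is zonal. Its hypothesis can be read as stating the conditions under which MPP should help, not as promising a comparison with unscarred ventricles. Fig. 2 contrasts lead sites, and the objective in Section 6 and the hypotheses in Section 12.3 are confined to peri-scar against remote. Whether benefit is related to position is an interaction, which the second comparison tests directly; a peri-scar test alone would not. Section 12.1 also says that proving significance is not the main aim.

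Much of this stands. A reader might infer that nothing in Section 3.1 is tested, which would be wrong: lead position is tested, and the gain in each zone is a listed outcome. A reader might also infer that MPP is expected to do worse than single-site pacing in remote tissue. The documents do not support that. Section 4 describes small and variable improvements, Section 12.1 a range from 0% to 40%, and neither reports a loss. The 0 v -8 and 0 v -5 cases show what the comparison cannot exclude; they are not forecasts.

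What does not fall is that the hypothesis in Section 3.1 compares MPP with single-site pacing near scar, no interval is planned for that comparison, and the question still names scar presence as a factor.

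**Conclusion.** The point holds as a gap between what Section 3.1 claims and what the design and Section 12.3 can deliver. The effect of scar presence is not estimable, with 0 scar-free patients out of 15; this follows from the eligibility criteria and needs no assumption. The claim that MPP is better near scar has no planned test or interval, and a between-zone difference alone cannot establish it. Under the assumed SD of 5 points and correlation 0.5, the zone test would be positive 95% of the time with gains of 0 and -5, and about 2.4% of the time with +5 in both zones. At SD 10 the first figure is 44%. These percentages rest on assumed values; the logical gap does not.

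It would be too strong to conclude that the pilot needs a rigid rule requiring both results to be significant. That is debatable with 15 patients, and the within-zone gain carries a small bias against MPP, so such a rule could reject a real effect. This is an inexpensive improvement to wording and reporting, not a fault in data collection.

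**What to change.** 1. **Section 3.1:** limit the question and hypothesis to lead position relative to scar in patients who have LV scar, and drop presence of scar as a factor under study.
2. **Section 12.3:** for each zone, add the mean percentage change in LV-dP/dTmax of best MPP over best single-site pacing, with its 95% CI. Interpret the between-zone result alongside the peri-scar interval, and state that MPP is better near scar only if that interval supports it.
3. **Selection bias:** note that best of 3 against best of 4 slightly disfavours MPP. Alternatively, use the repeat measurements in Section 9.2.4: choose the best configurations on one reading and estimate the gain on the other.

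The cost is protocol wording and two intervals from measurements already planned. The claim becomes narrower, and power to claim support for the hypothesis may fall. With true gains of +8 and 0, requiring both results would leave power above 99% at SD 5 but lower it from 82% to 71% at SD 10. Studying scar presence itself would need scar-free patients, which no analysis of this sample can replace.
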